## **III. Subject Participation**

**A. Recruitment:** Participants will be recruited through the KUMC's collaborator site (Swope Health Services), via posted fliers, Craigslist fliers, announcements, and word-of-mouth referrals. Once participants contact the study team, the project coordinator will reply with a brief description of the study procedures and try to schedule the individual's baseline session.

**B. Screening Interview/questionnaire:** Participants will be screened out using questionnaires if they indicate a severe substance use disorder according to the DSM-V with any substance other than tobacco or have any significant medical or psychiatric condition. Such conditions could include traumatic brain injury, dementia, significant learning disability, or psychotic symptoms. Participants will be consented prior to screening procedures.

### **C. Informed consent process and timing of obtaining of consent:**

1. The project coordinator ([name]) will give subjects detailed and comprehensive information about the study and obtain their written consent.
2. The project coordinator ([name]) will summarize study procedures, risks, compensations, and other relevant information to the participant. Then, the participant will be allowed to fully read the ICF in as much time as they need. The participant may ask questions at any point before or after reading the ICF, after which they will have the chance to sign the document. Participants will be given a copy for their records and will be able to withdraw their consent at any point without penalty.
3. Individuals who are cognitively or decisionally impaired (e.g., dementia, psychosis) will be screened out over a phone call prior to consent procedures. The project coordinator ([name]) will screen interested individuals over the phone.

**D. Alternatives to Participation:** The alternative to participation is to not participate.

**E. Costs to Subjects:** There will be no costs to participants during this study.

**F. How latest information will be conveyed to the study subject and how it will be documented:** Latest information regarding the participants in the study will be conveyed via email. This will be documented in a spreadsheet to ensure that all participants received all necessary information for the study.

**Payment, including a prorated plan for payment:** Participants will be compensated using a prepaid debit card (ClinCard) for their participation in this study. They will receive \$25.00 for completing all assessments at the baseline session. For the weekly training sessions, they will be receive a minimum of \$17.50 for every session they complete. If they complete at least 5 computer training sessions, they will receive \$10.00, and if they complete an additional 5 (i.e., all 10 session), they will be given an additional \$20.00. They will receive \$35.00 for completing the post-training session, \$30.00 for completing the 1-week post-quit date session, and \$30.00 for completing the 1-month post-quit date session. The payment for each of the assessment sessions reflects a \$10 amount to compensate individuals for transportation to the study site.

**A. Payment for a research-related injury:** N/A

#### **IV. Data Collection and Protection**

**A. Data Management and Security:** Data will primarily be collected using Qualtrics. Digital data files that contain identifiable information will be kept on a KU SharePoint site. Pictures of saliva sample test results will also be kept on the SharePoint.

1. The research team, including [name], [name], and [name] will have access for study data.

2. Data will be stored on a KU-owned SharePoint site. Only study staff will have access to the data for this study. All study data will be de-identified and given a numerical identification number.
3. Study staff will maintain a database with identifiable information of participants, but participants will be identified using a unique identifier throughout study participation.
4. All study team members will have access to the key code for de-identified data.
5. Each subject will get one numerical identification code that will be used only for this subject.
6. Data files will be maintained in a secure KU-owned SharePoint site.
7. Mobile devices will not be used for data collection or storage.
8. N/A.

**B. Sample / Specimen Collection:** Saliva samples will be collected using mouth swab tests, after which a picture will be taken of the test and the test will be discarded. The sample will be identified only by unique participant identifiers.

**C. Tissue Banking Considerations:** N/A

**D. Procedures to protect subject confidentiality:** Participant data will be coded with a numerical identification code and all data, including subject identifiers, ICFs, and contact information will be digitally stored on a KU-operated SharePoint folder (in addition to storage on Qualtrics). The data will be accessible only to study staff who are involved with the study. The data will be held for a maximum of 10 years after the primary results are published. After said period, all data will be erased.

**E. Quality Assurance / Monitoring**

1. The data will be updated every time a new participant is added to the study. Data collected and added will be checked using documents that the participant filled out to ensure that all data is correctly entered. All data will be checked weekly to ensure that the data is consistent and complete. Following any contact with a participant, additional information from the meeting will be added to the data.
2. There are no plans to have an ongoing third-party monitoring.

## **V. Data Analysis and Reporting**

**A. Statistical and Data Analysis:** Hypotheses encompassed within Aim 1 will be tested using Hierarchical Linear Modeling (HLM; Raudenbusch & Bryk, 2002), which allows the analysis of repeated measures and has been recommended because of its ability to: 1) accommodate missing data, 2) examine individual change over time in outcomes, and 3) include the average change and the individual variation around this average change which is especially important in a small sample (Raudenbusch & Bryk, 2002; Singer. & Willett, 2003), even in smaller samples (Collado et al., 2019).

- B. Outcome:** The study will conclude once we collect full data from 10 participants. It is expected that study hypotheses will be supported, with success/failure determined by results from WM training on cigarette use over time.
- C. Study results to participants:** Participants will be given information on their breath/saliva samples results immediately following testing if they are interested.
- D. Publication Plan:** Data will be used to support a subsequent NIH grant application. Attempts to publish in relevant peer-reviewed journal will made if hypotheses are sufficiently supported.

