**C. Sample size, statistical methods, and power calculation**

1. Consistent with Stage 1a pilot trials, the current trial included a small sample size of completers ( $N = 15$ ) to determine the initial outcomes of the WM intervention and its perceived feasibility/acceptability.
2. DD will be estimated by fitting the hyperbolic function specified in Eq. 1 to the indifference points computed during the task in order to estimate each individual's discount rate, where  $v$  represents the discounted value of an outcome,  $V$  is the undiscounted value,  $D$  is the delay and  $k$  is the discounting parameter, which specifies the degree to which the value of a given reward is discounted when it is delayed (with higher values representing greater discounting).

$$v = \frac{V}{1 + kD}$$

Eq. 1

While  $k$  distributions tend to be skewed, post-hoc natural logarithmic transformations will be performed, which have been shown to approximate normal distributions. We will calculate  $k$  values for each magnitude (\$50, \$200, \$1000). Due to varying degrees of goodness-of-fit associated with nonlinear regression functions, we will also calculate area-under-the-curve (AUC) estimates (Borges et al., 2016). Hypotheses encompassed will be tested using Hierarchical Linear Modeling (HLM; Raudenbusch & Bryk, 2002), which allows the analysis of repeated measures and has been recommended because of its ability to: 1) accommodate missing data, 2) examine individual change over time in outcomes, and 3) include the average change and the individual variation around this average change which is especially important

in a small sample (Raudenbusch & Bryk, 2002; Singer. & Willett, 2003), even in smaller samples (Collado et al., 2019). Hypotheses encompassed within Aim 1 will be tested using Hierarchical Linear Modeling (HLM; Raudenbusch & Bryk, 2002), which allows the analysis of repeated measures and has been recommended because of its ability to: 1) accommodate missing data, 2) examine individual change over time in outcomes, and 3) include the average change and the individual variation around this average change which is especially important in a small sample (Raudenbusch & Bryk, 2002; Singer. & Willett, 2003), even in smaller samples (Collado et al., 2019).

3. Individuals who smoke cigarette and who are low in SES and receptive to a future quit attempt will be recruited for this study. Participants will be recruited from the greater Kansas City area.

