4. Session 4 (quit week): Clinician will go over participants' use of the Daily Activity, Mood, and Smoking log, discuss quit dates and quitting experience (e.g., withdrawal and immediate plans) for each participant, discuss success in accomplishing LAVA activities, identify obstacles to abstinence, offer support, talk about maintaining a healthy lifestyle (i.e., proper diet and exercise), and highlight social support, particularly by encouraging participants to form a "Contract" with a supportive person in their life (i.e., ask someone to take part in an activity with them to help them remain abstinent, such as riding bicycles together).
5. Session 5: Clinician will go over participants' use of the Daily Activity, Mood, and Smoking log, participants' contracts, quitting experience (e.g., withdrawal symptoms), strategies to avoid smoking, perceived benefits and disadvantages to quitting smoking, and identifying high-risk situations.
6. Session 6: Clinician will go over participants' use of the Daily Activity, Mood, and Smoking log, quitting experience (e.g., withdrawal symptoms), strategies to avoid smoking, perceived benefits and disadvantages to quitting smoking, discuss time management as a tool for abstinence, help identify high-risk situations, and offer support.
7. Session 7: This session will mirror Session 6.
8. Session 8: This session will mirror Sessions 6 & 7, and will include a discussion on developing a post-program plan to maintain abstinence by engaging and monitoring activities after the BA group and dealing with negative feelings, triggers, and immediate cravings. The clinician will also review the overall program progress and remind participants about the upcoming follow-up sessions.

**Post-training session:** This session is expected to take 1 to 1.5 hours to complete. 2-3 days following their last training session, participants will complete the DD task, TLFB, TOH, HVLT-R, LNS, and provide a CO breath sample. Participants will be asked to set a quit date for their cigarette smoking at this session and will be encouraged to connect to the tobacco quitline ([name]).

**1-week post quit date session:** This session is expected to take about 30 minutes to complete. Around 7 days after their quit date, participants will complete the DD task, TLFB, and provide a CO breath sample. Participants will also provide a saliva sample to test for salivary cotinine, a metabolite of nicotine to biochemically verify smoking status/abstinence.

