**1-month post quit date session:** This session is expected to take about 45 minutes to complete. Around 30 days after their quit date, participants will complete the DD task, TLFB, TOH, HVLT-R, LNS, provide a CO breath sample, and provide a saliva sample.

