## **Measures**

**SCID DSM-5.** If a participant reports frequent drug or alcohol use, they will fill out questionnaires on their DSM-5 symptoms for the respective substance (other than tobacco). Data will be recorded on Qualtrics, only identified by participant ID.

*Wide Range Achievement Test 4 (WRAT 4).* A reading survey to measure participant's grade-level equivalent reading ability. This will be administered at the baseline session. Data will be recorded on paper, only identified by participant ID.

*Single Commodity Delay Discounting (DD).* A binary choice procedure will be conducted on a personal computer to assess DD. On each DD trial, two hypothetical money rewards will be presented on the screen. One outcome will be an amount of money available immediately; the other outcome will be a larger amount of money (\$50, \$1,000) available after some specified delay (1 week, 1 month, 6 months, 1 year, 5 years). Participants will indicate the preferred alternative with a mouse-click, and the computerized algorithm (Holt et al., 2003) will adjust the immediate reward over 6 trials to determine an indifference point for each amount/delay pairing, resulting in 7 indifference points (corresponding to the 7 delays) for each of 2 amounts (\$50\$1,000). Indifference points will be used to calculate delay discounting rates. Participants will be told to indicate preference on the task as if the outcomes were for real money; previous research has established the validity and reliability of DD tasks for hypothetical rewards (Matusiewicz et al., 2013). The results of this assessment will be recorded on a laptop computer, only identified by participant ID.

*Timeline Follow-Back (TLFB; Sobell & Sobell, 1992).* A 7-day TLFB methodology will be employed to assess point prevalence of tobacco use. Participants will be asked to report number of cigarettes smoked for each day. Participants will also be asked to report nicotine vape and marijuana use. Data will be recorded on Qualtrics, only identified by participant ID.

*Tower of Hanoi (ToH).* This assessment consists of a board with 3 pegs and 4 disks of differing sizes. Participants must move the stack of disks from one peg to another while following specific rules (i.e., all pegs must end up on the farthest peg and at no point can a larger disk be placed on top of a smaller disk). Task will be completed with a research assistant and data will be recorded on Qualtrics, only identified by participant ID.

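### If relapsers tend to miss the post-quit visits, HLM alone would overstate the fall in smoking, and the plan has no stated assumption or sensitivity analysis to show by how much

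*Combined protocol and SAP*

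**What the plan says.** Section V.A tests the hypotheses with HLM, "which allows the analysis of repeated measures and has been recommended because of its ability to: 1) accommodate missing data". Section II.C item 2 gives the same reason ("1) accommodate missing data"). There is no other text on missing outcomes: no missingness assumption, covariance structure, expected dropout, rule for a missed visit, or sensitivity analysis.

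Section V.B judges the trial on smoking, "with success/failure determined by results from WM training on cigarette use over time". The measure is self-reported cigarettes per day at study visits: "A 7-day TLFB methodology will be employed to assess point prevalence of tobacco use". Under Study Procedures there are two post-quit visits: "Around 7 days after their quit date, participants will complete the DD task, TLFB, and provide a CO breath sample", and later "Around 30 days after their quit date, participants will complete the DD task, TLFB, TOH, HVLT-R, LNS, provide a CO breath sample". Both also require a saliva sample. Section II.D item 3 allows withdrawal at any time and assigns no smoking status afterwards.

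The analysis set is not defined. Section II.C item 1 says "the current trial included a small sample size of completers", with N = 15, while section V.B ends the study at 10 participants with full data.

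**The concern.** A likelihood-based HLM uses every recorded value, but it is unbiased only if the chance of a missed visit depends on recorded values alone and the covariance model is adequate. After a quit date that is doubtful. Someone who has gone back to smoking has a reason to avoid a visit with breath and saliva tests. The last recorded value may predate the quit attempt, or be a zero at 1 week that gives no sign of a later relapse. The model then predicts the absent values largely from people who came.

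At stake is the outcome by which the plan judges success. With 10 to 15 participants, a few absent relapsers move the mean noticeably. Section V.D says the data will support a grant application, so an optimistic estimate would carry forward.

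**Working it through.** **What the plan supplies.** It gives four smoking assessments (baseline, post-training, 1 week, 1 month), a minimum of 4 cigarettes/day at entry, and N = 15 or 10. It gives no mean, SD, relapse rate, dropout rate or power calculation, so there is no figure to reproduce. The values below are assumptions.

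**Assumed inputs.** Baseline is about 12 cigarettes/day (SD about 4). Quitters fall by about 90%, and relapsers are back to about 85% of baseline at 1 month. The relapse share *r* is 40, 60 or 80%. A fraction *m* of relapsers (25, 50 or 75%) misses both post-quit visits.

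**Hand calculation.** Mean change is *a* = −0.90 × 12 = −10.8 in quitters and *b* = −0.15 × 12 = −1.8 in relapsers.

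- True change = (1 − r)a + rb
- Attenders' change = [(1 − r)a + r(1 − m)b] / (1 − rm)
- Missing set to baseline = attenders' change × (1 − rm)

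For r = 0.6 and m = 0.5:

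- True: −4.32 − 1.08 = −5.40
- Attenders: (−4.32 − 0.54) / 0.70 = −6.94
- Baseline replacement: −6.94 × 0.70 = −4.86

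**Simulation.** Each scenario had 4,000 participants. HLM was fitted by maximum likelihood with visit as a factor and a random intercept. Figures are change in cigarettes/day at 1 month; the true value varies slightly between runs by sampling.

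| Relapse / relapsers missing | Missing at 1 month | True | HLM | Completers only | Missing = baseline | HLM overstates by |
|---|---|---|---|---|---|---|
| 40% / 25% | 10% | −7.01 | −7.56 | −7.56 | −6.82 | 0.55 (8%) |
| 40% / 50% | 20% | −7.19 | −8.56 | −8.53 | −6.81 | 1.37 (19%) |
| 40% / 75% | 30% | −7.08 | −9.35 | −9.31 | −6.49 | 2.27 (32%) |
| 60% / 25% | 15% | −5.38 | −5.99 | −5.99 | −5.10 | 0.61 (11%) |
| 60% / 50% | 30% | −5.23 | −6.74 | −6.73 | −4.70 | 1.51 (29%) |
| 60% / 75% | 46% | −5.09 | −8.04 | −8.04 | −4.31 | 2.95 (58%) |
| 80% / 25% | 21% | −3.51 | −3.99 | −3.99 | −3.15 | 0.48 (14%) |
| 80% / 50% | 39% | −3.59 | −4.71 | −4.72 | −2.86 | 1.12 (31%) |
| 80% / 75% | 59% | −3.68 | −6.32 | −6.30 | −2.58 | 2.64 (72%) |

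An unstructured covariance gave results within 0.01 of the HLM column. HLM and completers-only agree closely because baseline and post-training smoking say little about who will relapse. In all nine rows the truth lies between HLM and baseline replacement. With 400 trials of N = 15 at 60% / 50%, the means were −5.40 true, −6.99 HLM and −4.84 baseline-replaced.

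**Other missingness mechanisms, at 60% relapse.**

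- Completely random: HLM −5.25 against a true −5.26, so no bias. Baseline replacement gave −3.71, which is too small.
- Dependent only on the observed 1-week value: unstructured −5.42 against a true −5.35, but random intercept −6.34. Missing at random is therefore not enough; the covariance model matters too.

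**Tipping point at 60% / 50%.** If absent participants smoke δ cigarettes/day more than HLM predicts, the estimate becomes −6.74 + 0.30δ. It reaches the true −5.23 at δ = 1.51 / 0.30 = 5.0. Baseline replacement equals the attenders' change times the fraction attending, so its sign is always that of the attenders' change. Asking only whether the two analyses agree in direction would therefore protect almost nothing.

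**The case against.** - **The mechanism may not arise.** The documents give no dropout rate, relapse rate or reason for missed visits. The payment section offers $30 for each post-quit session, for completing it and not for abstinence, which should reduce missed visits. This stands in part. It makes the direction conditional, but payment cannot show that the remaining absences are unrelated to smoking.
- **If only completers are analysed, HLM has no gaps to fill.** That is correct as a description, and the undefined analysis set leaves it possible. It does not remove the bias: completers-only gave −6.73 where HLM gave −6.74. It does mean that a sensitivity analysis works only if non-completers are in the analysis set.
- **This is a small exploratory pilot.** That argues for keeping the remedy light, and the remedy needs no new data.

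A reader might also infer that the quit rate will be inflated. The documents do not support that: HLM is applied to repeated measures, success rests on cigarette use over time, and no quit-rate analysis or denominator is proposed.

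**Conclusion.** The concern holds conditionally. The plan relies on HLM alone for missing outcomes, without stating the assumption this needs or testing departures from it. If relapsers preferentially miss post-quit visits, the 1-month reduction would be overstated, by about 0.5 to 3 cigarettes/day (roughly 8% to 70%) in the scenarios tried. Those figures depend on the assumed baseline level, relapse shares and missingness rates, and on relapsers missing both visits. A relapser who attends at 1 week and misses only 1 month would be partly corrected by a rich enough covariance model.

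It is tempting to conclude that this trial's reduction is overstated, or that a given percentage applies to it. Neither follows: with visits missing completely at random, HLM was unbiased, and the documents do not say which mechanism operates.

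**What to change.** 1. Define the analysis set as all enrolled participants with a baseline TLFB, not only completers, and reconcile the 15 with the 10.
2. State that HLM assumes missing at random, and specify the covariance structure and how time enters the model.
3. Pre-specify a sensitivity analysis that sets each missing post-quit TLFB to the participant's own baseline mean. If abstinence is reported, count missing CO or cotinine as smoking and keep everyone in the analysis set in the denominator. For example, 5 abstinent and 4 missing of 15 is 5/15 = 33%, not 5/11 = 45%.
4. Add a delta (tipping-point) analysis: report the excess smoking among absent participants at which the confidence interval reaches zero, or at which the reduction falls below a size named in advance.
5. Report both magnitudes and the numbers missing per visit, and base the conclusion on the bracket.

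The cost is SAP wording and a little extra analysis, with no new participants or visits. The downside is that baseline replacement is conservative, as the −3.71 against −5.26 under random missingness shows, so the reported reduction may look smaller. It belongs beside the HLM result, not in place of it.

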## II. Research Plan and Design

**A. Study Objectives:** The main aims of this project are to examine the observed efficacy of WM training.

**B. Study Type and Design:** This study is an open-label trial longitudinal (participants will be assessed through their 1-month quit date) trial.

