**Baseline session:** This session will take approximately 1 to 1.5 hour to complete and will include informed consent and initial assessments. Participants will complete an informed consent process, which will include time and space to read the informed consent form (ICF), followed by thorough discussion with a study staff member about the nature of the study, potential risks and benefits, and participant rights. If the individual wishes to continue following this discussion, they will digitally sign the ICF via Qualtrics. At the point at which the ICF is signed by the individual, s/he will be considered an enrolled participant. Participants will also report demographic information (age, sex, race/ethnicity, current income, employment, and education level) and report on their cigarette smoking behavior. If at any point during the study a participant reports elevated suicidality, they will be thoroughly assessed for suicidality risk by the PI, who has extensive clinical experience, and participants will be referred to immediate care (e.g., Emergency department, Kansas City crisis response) depending on level of risk. All individuals will be provided with a referral document which lists medical, substance use, and case management services in the Kansas City area. Participants will also complete a reading test (Wide Range Achievement Test-4; WRAT-4) to confirm reading level from self-reported educational attainment.

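### The stated sample is 15 completers, but the stop rule ends the study at 10 participants with full data, and the plan neither defines nor links the two counts

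*Combined protocol and SAP*

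**What the plan says.** **Sample size.** Section II.C, item 1, states that "the current trial included a small sample size of completers", with N given as 15. The only justification is that this is in keeping with Stage 1a pilot trials.

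**Stop rule.** Section V.B states: "The study will conclude once we collect full data from 10 participants". It adds that the study is judged on its result, with "success/failure determined by results from WM training on cigarette use over time".

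**Follow-up.** Section II.B says that "participants will be assessed through their 1-month quit date". Study Procedures places a post-training assessment first: "2-3 days following their last training session, participants will complete the DD task". The last visit comes later: "Around 30 days after their quit date, participants will complete the DD task, TLFB, TOH, HVLT-R, LNS". A person can therefore finish training without finishing follow-up.

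**Enrolment.** The baseline session text in Study Procedures says: "At the point at which the ICF is signed by the individual, s/he will be considered an enrolled participant". No enrolment target is given.

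**Analysis.** Sections II.C and V.A choose hierarchical linear modeling (HLM), "recommended because of its ability to: 1) accommodate missing data". Neither section says which participants enter the model.

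**The concern.** The 15 and the 10 are the only participant counts in the plan, and they sit in the two places where a reader looks for the size of the study. One describes the sample. The other says when data collection ends. The terms attached to them, *completers* and *full data*, are undefined and could be taken as the same thing. If they are the same, the stop rule is met before the stated sample is reached. If they differ, the plan does not say how.

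Two things are at stake. The first is precision: an estimate from 10 people is less certain than one from 15, and the verdict on cigarette use over time rests on whichever number holds. The second is interpretation: a reader cannot tell whether a study with 10 full records has met its plan, fallen short of it, or followed up 10 of 15 people who finished training.

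**Working it through.** **1. Can either number be reproduced?** No. The heading of section II.C mentions a power calculation, but none is given. The plan states no significance level, power, effect size, standard deviation or dropout rate. The two counts can only be set side by side.

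**2. The gap.** 15 − 10 = 5 participants, which is 5/15 = 33% of the stated sample or 5/10 = 50% of the stop-rule count.

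**3. Readings that would make the counts compatible.**

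- *Loss after training.* If 15 finish training and one third are then lost, 15 × (1 − 1/3) = 10 have full data. The arithmetic fits, and the visit schedule allows it, since the post-training and 1-month visits are separate. But the plan states no loss rate and does not say that *completers* means completers of training.
- *Planned and achieved.* Section II.C is in the past tense and section V.B in the future tense. Ten could be the planned end and 15 the number later reached, with only one section updated. No text reviewed says so.
- *The same count, one number out of date.* This is also possible and also unstated.

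**4. What the gap is worth (illustration).** Assumptions, none from the documents: one arm, a paired change from baseline, a two-sided 5% level, and only people with full data analysed. The half-width of the 95% confidence interval, in units of the SD of change, is t(0.975, n − 1)/√n.

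- n = 10: 2.262/√10 = 0.715, or 0.72 SD
- n = 15: 2.145/√15 = 0.554, or 0.55 SD
- Ratio: 0.715/0.554 = 1.29

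**5. Sensitivity to the single-arm assumption.** Study Procedures also describes a control training program but gives no allocation. If the participants were split evenly between two groups (a further assumption), the half-width for a difference in means is t(0.975, n₁ + n₂ − 2) × √(1/n₁ + 1/n₂).

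- 5 + 5: 2.306 × √(1/5 + 1/5) = 1.46 SD
- 7 + 8: 2.160 × √(1/7 + 1/8) = 1.12 SD

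The intervals are wider, but the comparison between 10 and 15 is similar.

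**6. Effect of the HLM.** If 15 people are trained, 10 have full data and the model uses all 15, the partial records recover some of the lost precision. How much depends on variances and on which visits are missed. The documents give neither, so no figure is offered.

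**The case against.** The strongest reply is that this is an ambiguity rather than a contradiction. The tenses differ, the two terms need not describe the same people, and at least one ordinary reading (15 trained, 10 fully followed) removes the conflict. This stands as far as it goes: the counts are not shown to be incompatible. But each such reading is conjecture, and each needs the same added sentence.

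A second reply is that little depends on it. Section I.C calls the hypotheses largely exploratory. Section II.C describes a Stage 1a pilot concerned with initial outcomes, feasibility and acceptability, and there is no power target for either number to miss. This also stands, and it limits the severity. The aims, visits, measures and model are unaffected.

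A third reply is that the 10 is a rule for ending the study and is never called an analysis set, while the choice of HLM for its handling of missing data leans against a completer-only analysis. That is right. The sentence on who enters the model is therefore a clarification and not the repair of an error.

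**Conclusion.** The point holds as an internal inconsistency of moderate severity. The plan states a sample of 15 completers, while its only sample-based stop rule is met at 10 people with full data. Following that rule therefore does not guarantee the stated sample. The shortfall can be five people with full data, and the interval half-width grows from 0.55 to 0.72 SD under the single-arm, paired-change assumptions above. That loss of precision is modest. The finding that nothing links the two counts rests on the text available for review, from which some parts had been removed.

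A reader might infer three stronger things that the documents do not support:

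- *That the 10 is the analysis set.* Section V.B does not say this, and the stated reason for HLM points the other way.
- *That the choice between 10 and 15 was left open so that it could follow the results.* No repeated or interim outcome analysis is planned. The biweekly review in section II.L belongs to safety monitoring.
- *That an error rate is compromised.* No confirmatory test or significance level is specified.

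**What to change.** Make sections II.C and V.B agree, in one of two ways:

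1. State one number of participants with full data through the 1-month visit, and use it in both sections. If the stop rule of 10 stands, restate the sample size in II.C as 10 with full data and accept the wider interval.
2. Keep both numbers, define *completers* and *full data*, say what each number counts (for example, 15 finishing training and 10 with full follow-up), and say which one ends the study.

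As a clarification in section V.A, add that the stop-rule count is not the analysis set and that every enrolled participant with any outcome data enters the HLM.

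The cost is wording in these sections, with no new visits or measures. The one practical cost arises if 15 with full data is the intended target: 15 − 10 = 5 more participants must then be followed to full data than the present stop rule requires.
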